Frequently sampled intravenous glucose tolerance test (FSIGT): All studies will be conducted in the follicular phase in controls and during amenorrhea in PCOS women. Each subject will be instructed to drink only water during the 12-hour fasting period before the FSIGT, and to avoid caffeinated fluid intake. Glucose in the form of a 50% solution (0.3 g/kg) and regular human insulin (0.03 units/kg) will be injected through an intravenous line at 0 and 20 min, respectively. Blood will be collected at -20, -15, -5, 0, 2, 4, 8, 19, 22, 30, 40, 50, 70, 90, and 180 min for glucose and insulin determinations. Approximately 2-3 tablespoons (28-42 ml) will be drawn for the FSIGT test. Adipocytes isolation and culture: Approximately 1.0 gm of fat will be obtained from the lower SC abdomen using standard procedures under local anesthesia. Adipocytes and the stromal vascular fraction will be isolated to measure adipocyte cell number and diameter, lipid accumulation and function, adiponectin, and stem cell development.

Procedures: All procedures will be performed in normal and PCOS women at the start of study.

i). Venipuncture: Fasting blood will be collected for blood count, chemistry panel, LH, FSH, total/free T, DHT, A4, DHEAS, E1, E2, anti-mullerian hormone (AMH), SHBG, adiponectin, IL-6,lipid profile, C-reactive protein, glucagon, leptin, C-peptide, and FFAs. Blood samples for all participants will be shipped to Oregon State Health University (OHSU) for analysis of AMH, IL-6, adiponectin, glucagon, leptin, and C-peptide levels. The University of Michigan will perform a comprehensive hormone analysis by LC-MS/MS, including traditional (T, AD, DHEA, DHEAS) and emerging androgen biomarkers (11-oxygenated C19 steroids, 11 OHA, 11KA, 11OHT, 11KT). There will be no personal identifiers on the samples that sent to OHSU or University of Michigan.

Study numbers will be used.

ii). Body composition: Body composition will be assessed by BMI, waist-to-hip circumference and DXA scanning. Girths will be measured at the waist (narrowest section of the torso between ribs and umbilicus) and hips (largest protrusion of the hip region, above the gluteal fold). For total body fat and regional fat distribution (central vs. appendicular), whole body scans will be performed, utilizing DXA imaging (Hologics QDR 1500). A portable BIA will calculate lean body mass changes by computerized methods to measure resistance and reactance.

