We will use one-way factorial analysis of variance (ANOVA) methods to compare continuous outcomes including hormone levels; adipocyte size, lipid content and glycerol release; numbers of ASCs and preadipocytes; mRNA levels. If data are not normally distributed on any scale, we will carry out nonparametric ANOVA.

Our previous comparison of cFOS gene expression in PCOS women vs. controls showed an increase in Δ Ct (6.0 ± 1.4). Based on this, we hypothesize that the mean difference between controls and IR PCOS is 1.7 SD units. Assuming this, a sample size of 8/group (IR vs. non-IR PCOS) provides over 80% power using the usual two-sided p < 0.05.

We also will compare all outcomes before vs. after 6 months of placebo or flutamide treatment controlling for IR status, using either the parametric paired t test or non-parametric Wilcoxon signed rank test. Insulin action and sensitivity will be assessed by calculating a Matsuda Index from blood glucose and insulin levels during the oral glucose tolerance test. Ovarian estradiol sensitivity to FSH will be calculated from the 24-hr area-under-the-curve (AUC) serum estradiol response to FSH infusion.

Based on our in vitro data, we observed a mean 0.17 log scale change in Δ Ct PPAR γ (SD=0.26 log units) after treatment with T + Flutamide vs. T alone. A sample size of 14 (7 non-IR, 7 IR) provides more than 80% power for the IR adjusted mean change.

REFERENCES

3. 2004. Revised 2003 consensus on diagnostic criteria and long-term health risks related to polycystic ovary syndrome. Fertil Steril 81(1):19-25.

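### About 45 to 50 outcomes are to be tested with no primary outcome and no multiplicity control, and nothing is designated to decide either Aim

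*Combined protocol and SAP*

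**What the plan says.** Statistical Considerations applies one-way ANOVA to continuous outcomes, introduced by the word including and so not a closed list: "hormone levels; adipocyte size, lipid content and glycerol release; numbers of ASCs and preadipocytes; mRNA levels". For Aim 2 it will "compare all outcomes before vs. after 6 months of placebo or flutamide treatment", using paired t or signed-rank tests.

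A significance level appears once, in the cFOS sample size sentence, where 8 per group "provides over 80% power using the usual two-sided p < 0.05". The PPAR-gamma sentence claims more than 80% power with 14 women and gives no level.

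The outcomes come from the procedures sections. Venipuncture alone lists "Fasting blood will be collected for blood count, chemistry panel, LH, FSH, total/free T, DHT, A4, DHEAS, E1, E2, anti-mullerian hormone (AMH" and then "SHBG, adiponectin, IL-6,lipid profile, C-reactive protein, glucagon, leptin, C-peptide, and FFAs". The LC-MS/MS panel adds DHEA and "emerging androgen biomarkers (11-oxygenated C19 steroids, 11 OHA, 11KA, 11OHT, 11KT". The fat biopsy yields "adipocyte cell number and diameter, lipid accumulation and function, adiponectin, and stem cell development". DXA, MRI, ovarian and insulin measures follow, and the baseline procedures are repeated in PCOS women after treatment.

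Under Aims and Objectives, each Aim carries one hypothesis about storage in subcutaneous abdominal fat: constrained in lean PCOS (Aim 1), normalised on flutamide (Aim 2). No measure is attached to either. No primary or secondary outcome, testing order or multiplicity rule was found. One stretch of the protocol, just before the amendment #42 text on epigenetic studies, was not available for this check.

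**The concern.** The two Aim hypotheses concern a construct, and several measures could stand for it: adipocyte size, lipid content, precursor cell numbers, gene expression, MRI subcutaneous fat. With no lead measure and no error control, whichever of these crosses 0.05 can be presented afterwards as the answer, and chance findings elsewhere cannot be told apart from the questions the study was built to answer. The planned completers are only 36 PCOS women and 12 controls, so this is a small sample for a long outcome list.

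The two power statements do not fill the gap. They concern cFOS and PPAR-gamma expression, neither marker is called primary, and both calculations rest on insulin-resistant and non-insulin-resistant groups.

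**Working it through.** **1. The plan's own power figures**

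*cFOS.* Inputs: difference 1.7 SD, 8 per group, two-sided 0.05. Noncentrality = 1.7 × √(8/2) = 3.40, with 14 degrees of freedom and critical t 2.145. Power is 88%, consistent with the stated figure of over 80%. However, the 1.7 SD is described as controls versus insulin-resistant PCOS, while the groups sized are insulin-resistant versus non-insulin-resistant PCOS.

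*PPAR-gamma.* Inputs: mean change 0.17, SD 0.26, n = 14. Standardised change = 0.17/0.26 = 0.654. Noncentrality = 0.654 × √14 = 2.45, with 13 degrees of freedom and critical t 2.160. Power is 62% (two-sided paired t), or 75% one-sided. This does not reproduce the stated figure; 21 women would be needed for 80% two-sided. The calculation takes 0.26 as the SD of the change, which is how the sentence reads. If it were the SD of a single measurement and the two measurements correlated at 0.7 (an assumption), the SD of the change would be 0.26 × √0.6 = 0.201 and power 83%.

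**2. Outcome count** (the documents give none)

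| Group | Source section | Count |
|---|---|---|
| Hormones LH to AMH | Venipuncture | 10 |
| SHBG to FFAs, lipid profile counted once | Venipuncture | 9 |
| DHEA and four 11-oxygenated steroids | Venipuncture | 5 |
| Adipocyte number, size, lipid, glycerol release, ASCs, preadipocytes, cFOS, PPAR-gamma | Adipocytes isolation; Statistical Considerations | 8 |
| BMI, waist-to-hip, BIA lean mass | Body composition | 3 |
| DXA measures | Body fat distribution | 6 |
| MRI subcutaneous and visceral fat | Body fat distribution | 2 |
| Ovarian volume, follicle number, E2 response with and without follicle adjustment, ovulatory frequency | Ovarian testing; Menstrual records | 5 |
| Insulin sensitivity | Statistical Considerations | 1 |
| **Total** | | **49** |

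The two Beck scales would make 51. Blood count, chemistry panel and the epigenetic assays are left out. Merging overlapping measures brings the total to about 45. Counting only the classes named in Statistical Considerations gives about 28.

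**3. Error rates if every test is read at 0.05**

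Expected false positives = 0.05 × number of true nulls: 0.05 × 40 = 2.0 and 0.05 × 45 = 2.25. This does not depend on correlation.

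Chance of at least one, independent tests = 1 − 0.95^k. For k = 28 it is 76%; for 40, 87%; for 45, 90%; for 49, 92%.

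With equal correlation between test statistics (assumed values, all nulls true):

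| Tests | 0 | 0.3 | 0.5 | 0.7 |
|---|---|---|---|---|
| 40 | 87% | 74% | 57% | 38% |
| 45 | 90% | 78% | 60% | 39% |

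If only 20 nulls are true, 1.0 false positive is expected and the independent figure is 64%.

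**4. Effect of naming one outcome per Aim**

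The error rate for the deciding test is 5% per Aim, or 1 − 0.95² = 9.75% across two independent Aims. Bonferroni over 40 tests (0.05/40 = 0.00125) would instead leave 33% power for the cFOS case at 8 per group, and 19% for the PPAR-gamma change with 18 women in an arm. The 18 assumes that the 36 completers split equally; the allocation ratio is not stated.

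**The case against.** The study is openly exploratory: it aims to learn about mechanisms and to find markers. Many outcomes are proper in such work, and false-discovery control is one option among several. That stands as a reason for the long list. It does not explain why neither Aim's hypothesis has a measure to decide it.

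Four stronger readings are tempting, and the documents do not support them.

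- *False positives are near certain.* One set of 45 tests gives 90% only if all are independent and all nulls true. These outcomes overlap: related androgens, fat by DXA and MRI, E2 response computed two ways. Pooling Aim 1 with both Aim 2 arms would give 3 × 2.25 = 6.75 expected and 1 − (1 − 0.60)³ = 94% at correlation 0.5, but that needs the same list and all nulls true in each set. BMI is a matching variable in Aim 1, and ovulatory frequency by weekly urine is collected only in treated women. The Background reports that flutamide lowers androgens and triglycerides, and controls are selected to have neither polycystic ovaries nor endocrine dysfunction. Some effects are therefore expected to be real.
- *The plan prescribes 0.05 for every test.* It does not say so. That level is inferred from one power sentence, although no other level is offered.
- *Almost any data set would support an Aim.* Both hypotheses are directional and concern subcutaneous abdominal fat, so a chance result for glucagon or LH supports neither. Taking eight relevant measures (an assumed set), the chance of a false positive in the predicted direction is 1 − 0.975^8 = 18% per comparison if independent.
- *cFOS and PPAR-gamma are in effect the primaries.* Their sizing uses insulin-resistance groups, whereas the amendment #29 text under Aim 2 says all PCOS women enrolled so far were non-insulin-resistant. The Aims never mention cFOS, and the PPAR-gamma inputs come from in vitro work.

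**Conclusion.** The concern holds in this form: about 45 to 50 outcomes, no primary, no multiplicity control, and no result designated to decide either storage hypothesis. If each test is read at 0.05, expect about two false positives per 40 to 45 true nulls in each comparison set, with a chance of at least one between about 40% and 90%, and fewer if some effects are real.

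This rests on an approximate outcome count, on 0.05 being applied throughout, and on assumed equal correlations of 0 to 0.7. The absence of a deciding outcome depends on none of these. The present power statements cannot be used to supply one. This is a cheap improvement to the analysis plan; nothing here invalidates the data being collected.

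**What to change.** Before the data are analysed or unblinded:

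1. The sponsor names one already-collected subcutaneous abdominal adipose measure per Aim as the deciding outcome. For Aim 1 the contrast is PCOS versus control. For Aim 2 it is the 6-month change, flutamide versus placebo; this must be stated because the present text describes only before-versus-after comparisons. Each is tested at two-sided 0.05.
2. Power is restated for those contrasts with the planned completers (36 PCOS, 12 controls), without carrying over the cFOS or PPAR-gamma figures. As an illustration, if the PPAR-gamma values (0.17, SD 0.26) were taken as a between-arm difference in change with 18 per arm, power would be about 48%.
3. All other outcomes are labelled exploratory, with Benjamini-Hochberg adjusted values beside the raw p-values within each Aim.

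The cost is a few sentences and one new power calculation, with no new data. The downside is that some nominally significant secondary results will not be declared as findings, and the restated power may prove low.

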The women with PCOS will be stratified according to whether they are insulin resistant or non insulin resistant based upon the results of their glucose tolerance test. Both groups will be randomized to receive the drug flutamide 125 mg/day or placebo. Subjects will take the drug/placebo every day for 6 - 28 day cycles and will continue to take the drug/placebo until all post treatment assessments are completed. Subjects will be asked to collect and store a urine sample once a week during the 6 - 28 day cycles. Subjects will also be asked to complete diaries. Once a month while they are taking the flutamide/placebo, they will return to the clinic and bring their urine samples. At that time they will undergo a physical exam, toxicity assessment, and blood draw. Quality of Life surveys will be performed at baseline, midpoint, and end of study for PCOS participants. Non-PCOS participants will complete Quality of Life surveys at baseline only.

After the 6 - 28 day cycles are completed the PCOS participants will continue to take study drug/placebo until they have completed end of treatment evaluations which include physical exam, additional blood tests, removal of abdominal fat, trasvaginal ovarian ultrasound, MRI, DXA scan, frequently-sampled intravenous glucose tolerance test (FSIGT), and follicle stimulating hormone stimulation test.

Per amendment #11 submitted 11-25-13, subjects who previously underwent an OGTT will be asked to undergo an FSIGT. Women enrolled on the PCOS arm may choose to decline the FSIGT and will undergo an OGTT post treatment.

Per Amendment #24 submitted 6/10/15, we requested permission to add a Family History Questionnaire to this study. Subjects who have been enrolled in the past as well as future participants will be asked to complete the questionnaire. Active study participants will be asked to complete the questionnaire at their next regularly scheduled study visit. Those who have completed all of their study visits will be contacted by phone or email to ask if they will complete the questionnaire. If they agree, it will be sent to the participant by US mail with a stamped return envelope or the questionnaire will be completed over the phone. New study participants will be asked to complete the questionnaire at their eligibility visit. If any participant(s) decline, their participation in Revised 3-7-18 UCLA IRB #12-001780 Page 3 of 27

this study will not be affected nor will their future healthcare at UCLA.

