BACKGROUND AND SIGNIFICANCE

Polycystic ovary syndrome (PCOS): PCOS, a common endocrinopathy affecting 6–10% of women, manifests by hyperandrogenism, ovulatory dysfunction and polycystic ovaries (PCO) in its complete phenotype. Abdominal adiposity occurs frequently in PCOS women vs. controls, including some, but not all, nonobese individuals. Consequently, the estimated prevalence of MBS in PCOS is 33-47%, about 2-3 times higher than that of age-matched controls.

Interplay between adipose function and androgen excess: In PCOS, intrinsic defects combine with endocrine factors to impair insulin sensitivity and induce adipocyte insulin resistance (IR). Conversely, physiological androgen administration to women induces IR. In PCOS women, therefore, androgen excess could decrease numbers of SC abdominal adipocytes and reduce capacity of this adipose to safely store fat. Thus, if energy intake exceeds this capacity, SC abdominal adipocytes would likely overfill with lipid to promote ectopic lipid deposition. We hypothesize that PCOS-related hyperandrogenism decreases adipogenic differentiation and increases adipocyte lipid content in a constrained SC abdominal adipose, inducing lipotoxicity, IR and ovulatory dysfunction.

Therefore, reducing PCOS-related androgen excess could improve SC abdominal adipogenic function and ovarian folliculogenesis, reducing use of ovulation-inducing agents in PCOS women wishing to conceive, and risks of multiple pregnancy.

Effect of flutamide on PCOS: Administration of flutamide, a nonsteroidal anti-androgen, to PCOS women lowers circulating androgen and triglycerides levels. Flutamide also restores ovulation in some, but not all, PCOS women. We will systematically compare SC abdominal adipogenesis, circulating adipogenic markers and SC abdominal as well as visceral (omental plus mesenteric) adipose content of lean PCOS women randomized to 6-month low-dose flutamide vs. placebo to determine how differences in key variables affect ovarian function and morphology, as well as in vivo E2 responsiveness to FSH.

We also are able to quantify SC abdominal and visceral adipose content by magnetic resonance imaging (MRI), as performed by [name]. Finally low-dose flutamide vs, placebo administration to lean PCOS women will discover novel molecular and biochemical markers that predict efficacy of androgen blockade in restoring adipogenic and ovarian function.

AIMS AND OBJECTIVES

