Subjects and clinical assessment: We will recruit subjects with the intention of enrolling 90 women - 70 lean (18.5-25 kg/M2) PCOS subjects and 20 age- and BMI-matched controls with the assumption that there will be dropouts such that 36 women with PCOS and 12 controls will complete the study. Subjects will complete a standardized questionnaire emphasizing menstrual dating, abnormal hair growth and acne. The questionnaire also will annotate age, smoking status, medications, surgical history and family histories of excess hair growth in female relatives and of diabetes in parents or siblings for exclusion criteria and for inclusion of some basic traits as covariates. Subjects also will undergo a physical examination; hirsutism will be scored by the modified Ferriman-Gallwey (mFG) method. Transvaginal sonography (TVUS) will be performed to determine the presence or absence of polycystic ovaries by Rotterdam

Revised 3-7-18 UCLA IRB #12-001780 Page 5 of 27

criterion. A screening blood sample will be obtained for determinations of steroid hormones, TSH, and prolactin; biochemical hyperandrogenism will be defined as an elevated serum total or free T > 2 SD above the mean value. Non-Hispanic Caucasian women between the ages of 18 and 35 years will be recruited to avoid confounding differences as a function of race. PCOS patients will be diagnosed by 1990 NIH criteria. Controls will have regular menstrual cycles at 21 to 35 day intervals, a luteal phase progesterone (P4) level > 3 ng/mL, and no evidence of hirsutism, acne, alopecia, polycystic ovaries or endocrine dysfunction. Exclusion criteria are: present/past history of smoking during the past year, cancer, alcohol abuse, drug addiction, severe depression, or post traumatic stress; diabetes; uncontrolled hypertension (\geq 165/100); clinically significant hepatic or renal disease, or other major medical illness; signs or symptoms of infection; recent (within 30 days) use of an experimental device; recent (within 6 months) use of androgens, anabolic steroids or non-steroidal anti-inflammatory drugs; recent (within 3 months) use of hormonal agents (including birth control pills, Plan B, Mirena IUD, or insulin sensitizers); use of the drug warfarin; beta blockers; CYP active medications or herbs.

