iii). Body fat distribution: Total body DXA will measure abdominal fat (i.e., the area between the dome of the diaphragm [cephalad limit] and the top of the greater trochanter [caudal limit]). Total body DEXA images also will determine % body fat; fatfree body mass; total body, abdominal, and leg fat; and abdomen/leg fat mass ratio. The leg region is that area below the top of the greater trochanter. Multiple axial abdominal and pelvic MRI slices from the diaphragm to the pelvis will assess cross-sectional areas of SC abdominal and visceral fat.

iv). Ovarian testing:

a). Ovarian morphology: TVUS using a 4- to 8-mHz vaginal probe will be performed in the follicular phase in controls and during amenorrhea in PCOS women. Summed ovarian volume will be calculated. Antral follicle number, defined as the total follicle number (2-9 mm in diameter) of both ovaries, will be determined by 1 investigator ([name]). Polycystic ovaries will be defined by 12 or more follicles in each ovary measuring 2-9 mm in diameter, and/or increased ovarian volume (> 10 ml), with one such ovary sufficient to define PCO.

b). E2 response to recombinant human (rh)FSH. Blood samples will be drawn through an indwelling iv catheter at -90, -60, -30 minutes and time 0 as well as 0.5, 1, 1.5, 2, 3, 4, 6, 8, 10, 12, 16, 20, and 24 h after 150 U rhFSH injection (112). The E2 response to rhFSH will be assessed before and after adjusting for numbers of TVUS-detected ovarian antral follicles.

Aim 2. Examine effect of flutamide in lean PCOS women on SC abdominal adipogenesis, visceral adipose content and ovarian folliculogenesis.

Per amendment #29, we are requesting permission to change the randomization strategy since all PCOS subjects enrolled thus far have been non-insulin resistant

Revised 3-7-18 UCLA IRB #12-001780 Page 7 of 27

based upon the results of the Frequently Sampled Intravenous Glucose Tolerance Test. Therefore, the need to stratify the PCOS subjects into two groups (i.e. insulin resistant versus non-insulin resistant) is unnecessary. All PCOS subjects recruited will now be randomized to study drug versus placebo based upon non-insulin resistant status. Of note, the control subjects are not randomized since they do not receive study drug or placebo.

Adipogenic studies: All adipogenic studies performed at study initiation will be repeated at the end of the 6 - 28 day cycles of flutamide vs. placebo intervention in PCOS women.

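### The before-after analysis promises control for insulin-resistance status, but the named tests take no covariate and every PCOS woman enrolled so far is in the same category

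*Combined protocol and SAP*

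**What the plan says.** Three places in the protocol bear on this.

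- **Statistical Considerations.** "We also will compare all outcomes before vs. after 6 months of placebo or flutamide treatment", with the qualifier "controlling for IR status, using either the parametric paired t test or non-parametric Wilcoxon signed rank test". The section then claims more than 80% power for an IR-adjusted mean change with 14 women, 7 non-IR and 7 IR. It names no regression or covariance model. Its insulin-sensitivity measure is a Matsuda index from the oral glucose tolerance test (OGTT).
- **Research Design and Methods, Aim 2.** Citing amendment #29, the current text reports that "all PCOS subjects enrolled thus far have been non-insulin resistant" on the intravenous test (FSIGT) and calls IR stratification unnecessary. It continues: "All PCOS subjects recruited will now be randomized to study drug versus placebo based upon non-insulin resistant status".
- **Lay Summary.** "The women with PCOS will be stratified according to whether they are insulin resistant or non insulin resistant", with both groups then randomized.

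Covariates are mentioned once more, under Subjects and clinical assessment. Questionnaire items are collected partly "for inclusion of some basic traits as covariates", with no model named and no reference to insulin sensitivity.

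**The concern.** The analysis sentence promises an adjustment and names two methods that cannot make one. The factor to be adjusted for also has a single level among the PCOS women enrolled when amendment #29 was written, and later recruits are to be randomized on the same non-IR basis. An analyst following the plan would run plain paired tests and could report them as IR-adjusted. The power statement describes a half-IR sample that the trial no longer plans to recruit.

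The sentence is also the only one that sets out an analysis of the 6-month data, and it compares before with after. Aim 2 concerns the effect of flutamide, and the women are randomized to flutamide or placebo. The one-way ANOVA sentence does not say which groups it compares. The baseline values that would sharpen a between-arm comparison are already collected, but the plan gives them no role in one.

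**Working it through.** **1. The plan's own figure.** The inputs, all from Statistical Considerations, are a mean change of 0.17, SD 0.26 and n = 14. A test "using the usual two-sided p < 0.05" is stated for the other power calculation and assumed here. Reading 0.26 as the SD of the change:

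- d = 0.17/0.26 = 0.654; noncentrality = 0.654 × √14 = 2.45.
- Two-sided paired t, 13 df: power 61.9%. With one IR term, 12 df: 61.3%.
- Two-sided normal approximation: 68.7%. One-sided t: 74.9%.

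None reaches the stated 80%. If 0.26 were the SD of a single measurement, 80% would need a before-after correlation of about 0.67, which the documents do not give. This shortfall is a separate matter. What counts here is that the calculation presupposes two IR strata of 7.

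**2. What controlling for IR could mean.** Write each woman's change as μ + β × IR + error.

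- With 7 non-IR and 7 IR women the design matrix has rank 2. The adjusted mean is the average of the two stratum means, with 12 df.
- With every woman non-IR, the IR column is constant and the rank is 1. β cannot be estimated, and the estimate of μ is the ordinary mean change with n − 1 df.

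The second case is the plain paired t test. The signed-rank test likewise has no IR term.

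**3. What a continuous covariate would do.** Assume that the 36 PCOS completers (Subjects and clinical assessment) split 18/18; the ratio is not stated. Let r be the correlation between baseline insulin sensitivity and the outcome after allowing for the outcome's own baseline. With k added terms and N = 36, the SE of the flutamide-placebo difference is multiplied by

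√(1 − r²) × √(1 + k/(N − k − 3)).

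For k = 1 (insulin sensitivity) the second factor is √(1 + 1/32) = 1.016. For k = 2 (also an indicator for OGTT versus FSIGT, assumed to explain nothing further) it is √(1 + 2/31) = 1.032.

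| r | √(1 − r²) | k = 1 | k = 2 |
|---|---|---|---|
| 0 | 1.000 | 1.016 (+1.6%) | 1.032 (+3.2%) |
| 0.3 | 0.954 | 0.969 (−3%) | 0.984 (−1.6%) |
| 0.5 | 0.866 | 0.879 (−12%) | 0.894 (−11%) |

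Counting the outcome's own baseline as already in the model makes the second factors √(32/31) = 1.016 and √(32/30) = 1.033, a difference of at most about 0.1 percentage point. The terms pay for themselves only when r² exceeds 1/33 (r about 0.17) for k = 1, or 2/33 (r about 0.25) for k = 2.

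**4. Within one arm.** With a centred covariate, the fitted mean change equals the sample mean change, and its variance over repeated samples is unchanged. The table therefore applies only to the comparison of arms.

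**The case against.** The best defence is that the sentence was written for two IR strata. Averaging paired changes over strata is a legitimate form of control, and with one stratum it reduces to the plain paired test. IR status is then controlled by restriction, and pairing removes each woman's fixed level. This stands as far as bias is concerned: losing the IR term does not distort the within-arm mean change. It does not rescue the wording, because no adjustment is made and the 7 + 7 sample is not the one described under Aim 2.

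A second defence is that adjustment for a prognostic covariate is optional in a randomized trial. That also stands. In lean women who are all classed as non-IR, the restricted range would tend to lower r. The Background lists IR as a result of constrained adipose tissue ("inducing lipotoxicity, IR and ovulatory dysfunction"), which does not make it a predictor of response to treatment.

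A reader might infer four stronger things that the documents do not support:

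- **That baseline insulin sensitivity goes unused.** Aim 1 correlates key factors with insulin action in vivo, and insulin sensitivity is itself measured before and after treatment. It is only not a covariate in this analysis.
- **That every woman is known to be non-IR.** The statement covers those enrolled up to amendment #29, on FSIGT results. Women with only an OGTT are not covered by it, and for later recruits it is implied rather than guaranteed.
- **That the results are biased.** They are mislabelled.
- **That a large gain in precision is being forgone.** That needs r near 0.5 or above, and the documents give no value.

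**Conclusion.** The concern holds in a limited form. The promised control for IR status does not take place, for two independent reasons: the tests have no covariate term, and the factor has one level in the women enrolled so far. The IR-adjusted label and the 7 + 7 power statement are therefore wrong for the trial as it now stands, and Statistical Considerations and the Lay Summary conflict with the Aim 2 text. That part rests on the wording alone.

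The benefit of using baseline insulin sensitivity is conditional. It rests on an assumed 18/18 split and an unknown r, and ranges from a loss of 1.6% to 3.2% in SE at r = 0 to a gain of 11% to 12% at r = 0.5. It belongs to a flutamide-placebo contrast that the criticized sentence does not specify. The point should be corrected before analysis, but it does not threaten the validity of the within-arm estimates.

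**What to change.** - Delete the phrase about controlling for IR status and the IR-adjusted label. Restate the power statement for the sample now being recruited.
- Reconcile the Lay Summary, the Aim 2 design text and Statistical Considerations on whether IR strata exist.
- Compare flutamide with placebo by a linear model for the 6-month value, with treatment arm and the outcome's own baseline value. Where residuals are clearly non-normal, use a rank or permutation version of the same model.
- Optionally, prespecify baseline insulin sensitivity as a centred continuous covariate. Leave it out as a separate term when insulin sensitivity is the outcome, because it would then duplicate the baseline value. First reconcile the OGTT-based Matsuda wording with the FSIGT: name the FSIGT index (the plan names none) and say how OGTT-only women are handled. Their number is not given, and standardizing within test type is unstable if they are few.

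The change is to text only and needs no new measurement. The optional covariate costs about 1.6% in SE if it proves unrelated to the outcome, or 3.2% with a test-type indicator.
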